STUDY PROTOCOL

Full project title: *Changes in outcomes of treatment for adolescent anorexia nervosa after implementation of Family Based Treatment in a Norwegian child and adolescent mental health service: A retrospective cohort study with prospective follow-up*

Short project title and acronym: *Akershus university hospital retrospective cohort study of family based treatment / ARCS-FBT*

Short Norwegian title for public communication: *Familiebehandling av anoreksi – effekt og erfaringer med innføring av FBT-modellen*

SUMMARY

A two-group retrospective exploratory cohort study with longitudinal follow-up comparing adolescents with anorexia nervosa treated with generic family therapy to those treated with the manualised Family Based Treatment (FBT). The primary aim is to investigate whether adoption of FBT has led to faster normalisation of weight and lower rates of eating disorder in early adulthood. Secondary aims are to investigate whether implementation of FBT has changed the time to discharge, heterogeneity of patient weight change across treatment, rates of adverse events, rates of readmission, patient experiences of the treatment, long term functional outcomes and mortality. Data are extracted from patient health records, reported by participants and extracted from public registries.

STUDY MANAGEMENT AND RESEARCH GROUP

This study will be conducted by the Department of child and adolescent mental health services at Akershus university hospital. Director of research and innovation, professor [name], is responsible for research at Akershus university hospital. Head of Department [name] has the administrative responsibility for the project on behalf of the hospital.

Project manager and principal investigator:

[name]

Clinical psychologist, Department of child and adolescent mental health services

Project group:

[name]

Consultant, Department of child and adolescent mental health services

[name]

Senior researcher, Department of research and development in mental health

[name], MPhil

Research coordinator, Department of child and adolescent mental health services

BACKGROUND

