Adolescent anorexia nervosa is a severe eating disorder related to long-lasting morbidity and premature mortality (1, 2), and recent reports from hospitals suggests the prevalence in Norway may be increasing (3). The manualised family therapy “Family Based Treatment” (FBT) is currently the treatment approach for adolescent anorexia nervosa with the largest evidence base (4). FBT is recommended as a first line treatment in multiple service contexts (5, 6).

While there has been conducted several randomised controlled trials of FBT in academic settings (7), there are few large studies examining outcomes when FBT is implemented in clinical practice. A

systematic review published in 2015 found five such dissemination studies. Of these, three were conducted in academic clinical settings with the number of patients ranging from 11 to 20, and two were retrospective studies reporting changes in service use patterns after implementation of FBT in a regular mental health service (8). Two later studies have compared the outcomes achieved in clinical trials of FBT to those of FBT provided in regular clinical care, finding these to be comparable (9, 10), but these have both been conducted in highly specialised clinical contexts. More studies with higher power are needed to confirm the effectiveness of FBT when disseminated to regular healthcare contexts.

At the Child and Adolescent Mental Health Service (CAMHS) unit Nedre Romerike BUP, adolescent anorexia nervosa has consistently been treated with family therapy for about 20 years. In 2018 the unit implemented FBT, making several changes to the form of family therapy provided. As part of treatment monitoring, patients are weighed regularly, and weight data are recorded in patient health records.

Restrictive eating and corresponding weight loss are core features of anorexia nervosa, besides distorted views of the body and rigid preoccupation with losing weight and avoiding weight gain. Normalisation of eating behaviour and weight status is hence the primary treatment goal, making the patient health records in this case contain relevant outcome data.

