The long-term course of anorexia nervosa is heterogeneous, and in some patients the disorder shows a protracted course, with long term morbidity and functional impairment, as well as increased mortality (11). There are few longitudinal studies of treatment outcomes with long follow-up periods (12). As Norway has a general system of personal identification numbers, following up patients across multiple public registries is a viable way to assess long term outcomes without the patients needing to participate in reporting.

AIMS

The primary aim is to assess the short and long-term effectiveness of FBT compared with non-manualised family therapy. This is operationalised as testing whether the adoption of FBT has led to patients achieving normalisation of weight faster than with the previously delivered family therapy, and whether it will lead to less treatment provided for eating disorders in adulthood. Secondary aims are to assess whether adoption of FBT have resulted in reduced time to discharge, changed the heterogeneity of weight gain across patients, whether there have been changes in the rates of adverse events and readmissions, and to assess whether the implementation of FBT has led to changes in long-term functional status and rate of mortality.

DESIGN AND METHODS

Participants and recruitment

This is a two-group retrospective exploratory cohort study with prospective longitudinal follow-up in public registries. Eligible participants are all patients initiating treatment during the years 2015-2020 with the eating disorder team at Nedre Romerike BUP with a primary ICD-10 diagnosis of F50.0 Anorexia nervosa or F50.1 Atypical anorexia nervosa. Patients will be excluded if they were treated during the years 2018-2020 and FBT was never initiated. It is estimated that the final sample size will be approximately 200.

Eligible participants will be identified through review of patient health records. Participants will be contacted by letter with information about the study, including a link to an online video explaining more about the study. Study personnel will make a follow-up telephone call approximately a week later to allow the eligible participant to ask any questions they may have before deciding on participation in the study. Participants who are interested in participating will be directed to a website

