where they can sign an electronic consent form and complete a short survey about their experience of treatment. The consent form and treatment experience survey will be implemented in “Tjenester for Sensitive Data”, which has appropriate security and allows for verified electronic signatures.

Participants will be contacted after they have reached age 16, and thus are able to give informed consent. They will be encouraged to discuss participation with their parents or other legal guardians.

Endpoints and data collection

Primary endpoint for the retrospective study is weight restoration, defined by patients having a weight measurement placing them at or above 95% of expected body weight (50. percentile) for age given Norwegian population norms, following established definitions of weight restoration (10).

Secondary endpoints are discharge from treatment and readmission to treatment (the latter is assumed to be right-censored).

Adverse events will be defined as debut of suicidal ideation, attempted suicide, debut of self-harming behaviour, severe self-harm where medical attention is indicated, hospitalisation for low weight or medical complications from low weight, admission to inpatient treatment for anorexia nervosa, involuntary gastric tube feeding, parental separation, and initiation of contact with child protective services.

Participant experiences and satisfaction with services will be assessed using the Generic Short Patient Experiences Questionnaire (GS-PEQ) (13).

The primary endpoint for the prospective study is continued morbidity, defined as being currently in treatment in specialist health care for any eating disorder. Secondary endpoints are mortality, level of education and employment status.

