This study does not involve any direct experimental manipulation, and as long as the process of extracting and analysing data from patient health records and public registries is conducted with due care, there is no risk of harm to the participants. FBT has been widely implemented in Norwegian health care based on findings from experimental studies in treatment settings quite different from regular public healthcare services. Research on the short and long-term effectiveness of FBT in a Norwegian context hence has considerable value to society and future patients receiving treatment for anorexia nervosa.

STUDY TIMELINE AND PLANS FOR DISSEMINATION

The study was approved with qualifications by the Regional Ethics Committee in 2021 with a requirement to adjust the protocol to seek informed consent from all participants or their legal guardians. Final approval was granted in July 2022. The process of identifying and contacting eligible participants will start as soon as approval is received.

Data extraction for the retrospective part of the study will start for each participant as soon as informed consent is obtained. It is expected to be finished at the latest in the fourth quarter of 2023, with reliability checking completed within 2023. Preparation of computer code for analysis will be done concurrently, and analysis will commence when data extraction is completed. Preparation of reports

for publication will be done during 2023 and early 2024. Findings will be submitted to international scientific journals specialising in eating disorders. Abbreviated reports of findings will also be prepared and submitted to the journals of relevant Norwegian professional associations.

For the prospective part of the study data will be extracted in four waves, when the participant last initiating treatment has reached the planned time for follow-up and registries are updated. An individual follow-up date will be calculated for each participant, to adjust for differences in when participants initiated treatment, and the closest relevant registry entry to that date will be extracted. The project group will consult with the agencies maintaining the registries to plan data extraction in detail. Findings from the prospective part of the study will be reported in international scientific journals as they become available.

DATA RETENTION

Documentation for the clinical study will be retained for five years after final study report/publication.

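### Patient experience is surveyed once, at consent, so recall time is heavily confounded with cohort and a GS-PEQ difference cannot credibly be attributed to FBT as planned

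*Combined protocol and SAP*

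**What the plan says.** The Summary lists, among the things that implementing FBT may have altered, "rates of readmission, patient experiences of the treatment, long term functional outcomes and mortality". The Aims section does not repeat patient experience.

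Under Participants and recruitment, "Eligible participants are all patients initiating treatment during the years 2015-2020". The Background places the change of treatment in time: "In 2018 the unit implemented FBT, making several changes to the form of family therapy provided". The exclusion rule also treats 2018 to 2020 as the FBT years: "Patients will be excluded if they were treated during the years 2018-2020 and FBT was never initiated".

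Interested participants are sent to a website "where they can sign an electronic consent form and complete a short survey about their experience of treatment". Endpoints and data collection names GS-PEQ as the instrument. No survey at discharge, or at a fixed time after treatment, is described.

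On timing, the Study timeline section states: "Final approval was granted in July 2022". Contact follows approval, each participant's extraction follows consent, and extraction is due to finish by the fourth quarter of 2023.

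The Analysis plan gives no model for GS-PEQ. The covariates it names belong to the survival models and include neither survey date nor time since treatment.

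**The concern.** All participants are surveyed in roughly the same calendar window, but the two cohorts were treated in successive calendar periods. The earlier cohort must look back further, so the length of recall is largely set by which treatment a participant received.

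A difference in GS-PEQ scores could then reflect the treatment, fading memory, hindsight about how the illness turned out, or care received since. The documents give no basis for the direction of the bias, so a reader could not discount the result by a known amount. A larger sample would not help, because the problem lies in the timing.

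There is also a smaller ambiguity about what is being rated. The protocol expects some readmissions. A patient who began in 2015 to 2017 and was readmitted after FBT was introduced might rate the earlier therapy, FBT, or both.

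What is at stake is one secondary aim. Weight, discharge, adverse events and the registry outcomes come from records and are not exposed to recall.

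**Working it through.** The protocol states no recall interval and no sample-size figure for GS-PEQ, so there is no stated figure to reproduce.

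**Inputs**
- Starts: 2015.0 to 2021.0 (Participants and recruitment).
- Cohort boundary: 2018.0. This is assumed, since the Background gives only the year.
- Survey window: 2022.5 to 2024.0. This is inferred from the approval date and the planned end of extraction; no survey dates are stated.
- Starts and surveys evenly spread (assumption).

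**Recall from treatment start = survey date − start date**
- Before FBT: shortest 2022.5 − 2018.0 = 4.5 years; longest 2024.0 − 2015.0 = 9.0; mean 2023.25 − 2016.5 = 6.75.
- FBT: shortest 2022.5 − 2021.0 = 1.5 years; longest 2024.0 − 2018.0 = 6.0; mean 2023.25 − 2019.5 = 3.75.
- Gap: 6.75 − 3.75 = 3.0 years.

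**How far the gap depends on the assumptions**
- Survey dates: the gap is still 3.0 years if every survey falls in July 2022 (6.0 against 3.0) or at the end of 2023 (7.5 against 4.5).
- Boundary: for a boundary b, the gap in mean start date is (b + 2021)/2 − (2015 + b)/2 = 3.0, so a later switch within 2018 does not change it under even starts.
- Contact only from age 16: with assumed start ages spread over 11–18, 12–17 or 13–18, simulation gives a gap of about 2.8 to 3.0 years.
- Recall from discharge: gap = 3.0 + (mean FBT duration − mean pre-FBT duration). Durations are not in the documents. If FBT were between 1 year shorter and 0.5 year longer (assumed), the gap would be 2.0 to 3.5 years.

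**How closely recall follows cohort (equal cohort sizes assumed)**
- Between-cohort variance of recall: 1.5² = 2.25.
- Within-cohort variance, surveys spread over the window: 3²/12 + 1.5²/12 = 0.75 + 0.1875 = 0.9375.
- R² = 2.25/(2.25 + 0.9375) = 0.71, so |r| = 0.84 and variance inflation = 1/(1 − 0.71) ≈ 3.4.
- All surveys on one date: R² = 2.25/(2.25 + 0.75) = 0.75, |r| = 0.87, variance inflation 4.0.

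**Overlap in recall**
- The shared range is 4.5 to 6.0 years. With surveys spread, the share of each cohort inside it is (1.5²/2)/(1.5 × 3) = 1.125/4.5 = 25%. With all surveys on one date it is about 0%.
- Restricting to that range does not equalise recall. A simulation under the same assumptions gives means of 5.5 and 5.0 years, still 0.5 year apart.
- Comparing only 2017 with 2018 starters leaves a mean gap of 2018.5 − 2017.5 = 1.0 year. About one third of each group lies outside the shared range. Inside it, simulation gives means of 5.46 and 5.04 years, a gap of about 0.4 year.

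**The case against.** The strongest reply is that unequal recall is inherent in any retrospective before-and-after survey. The study calls itself exploratory, and patient experience appears as an aim only in the Summary. That stands, and it keeps this a point about one secondary claim. It does not remove the point, because the Summary still frames the outcome as a change brought about by FBT.

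The size of the gap rests on inferred dates, and time since discharge is the better measure for rating a course of care. This also stands. That there is a gap is well supported; its exact length is not.

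Three stronger readings are tempting and are not supported.
- A reader might infer that the contrast can show nothing. Recall and cohort are not perfectly collinear (R² 0.71 with surveys spread), and up to about 25% of each cohort shares a recall range. The confounding is heavy, not total.
- A reader might infer that the plan will report a GS-PEQ difference as caused by FBT. The protocol gives no GS-PEQ analysis and does not say how a difference would be reported.
- A reader might infer that ratings are contaminated by readmissions. The survey text is not in the documents, no readmission rate is given, and the survey may already name the course to be rated. This is a possibility only.

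**Conclusion.** The concern holds in this form: with one survey at consent, recall time is heavily confounded with cohort, and as planned a GS-PEQ difference cannot credibly be attributed to FBT. The gap is about 3 years from treatment start (6.75 against 3.75), given even recruitment, a 2018 boundary and surveys between July 2022 and the end of 2023. From discharge, its size cannot be fixed from the documents. How much a given gap shifts GS-PEQ scores, and in which direction, is also unknown. The point is worth acting on because it changes what the study may conclude on this aim and is cheap to correct. It does not touch the primary endpoints or any outcome taken from records or registries.

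**What to change.** 1. Have the survey ask about the index treatment course, meaning the first start in 2015 to 2020, if it does not already, and keep the survey date. If surveys are already complete, flag participants with a readmission, using the dates that are being extracted anyway.
2. In the Summary, take patient experience out of the list of outcomes that FBT implementation may have changed. Report GS-PEQ descriptively by cohort, beside the distribution of time from discharge to survey.
3. If a cohort contrast is shown, present it as a sensitivity analysis adjusted for time since discharge. State that it relies on limited overlap and a model assumption, and do not read it as an effect of FBT.

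Restricting the contrast to 2017 and 2018 starters is not a remedy. Recall still differs between those groups, and the overlap nearly vanishes if surveys cluster on one date.

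The cost is protocol wording, at most one line of survey instruction, and a retained date. Discharge and readmission dates are already in the extraction plan. The downside is a weaker claim for one secondary aim.

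### Contact only from age 16, with extraction expected to finish in 2023, sets a higher minimum age at treatment start in the FBT cohort (10-13 years) than in the earlier cohort (7-10 years)

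*Combined protocol and SAP*

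**What the plan says.** Under 'Participants and recruitment', the protocol states: "Eligible participants are all patients initiating treatment during the years 2015-2020". The Background gives the boundary between the cohorts: "In 2018 the unit implemented FBT, making several changes to the form of family therapy provided". The exclusion rule uses the same years: "Patients will be excluded if they were treated during the years 2018-2020 and FBT was never initiated".

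Recruitment depends on the patient's own consent: "Participants will be contacted after they have reached age 16, and thus are able to give informed consent". The only role described for parents is discussion with the participant.

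'Study timeline and plans for dissemination' supplies the dates. "Final approval was granted in July 2022", and contact was to begin once approval was received. Then: "Data extraction for the retrospective part of the study will start for each participant as soon as informed consent is obtained". Of that extraction it says: "It is expected to be finished at the latest in the fourth quarter of 2023". The same section records an ethics committee requirement to "seek informed consent from all participants or their legal guardians".

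The analysis plan first describes a survival model for days to weight restoration without naming covariates. It then adds models that include age among the covariates and examine it as a moderator. It does not say which of these is the main comparison. The protocol does not mention that the age-16 rule acts differently on the two cohorts, and it plans no comparison of eligible with included patients.

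**The concern.** The age-16 rule is worded identically for everyone, but the time available to reach 16 is not. A patient who started in January 2015 has nine years to reach 16 by the end of 2023; one who started in December 2020 has three. The effective age floor at treatment start therefore rises with calendar time, and calendar time is what separates the two cohorts.

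This selection comes from the study's own procedure, not from a change in the clinic's patients. Age plausibly matters for the outcomes. The plan lists it as a covariate and candidate moderator, and the weight-restoration endpoint is defined relative to weight expected for age. Follow-up dates in the registry part are set individually from treatment start, so age at start carries through to age at follow-up, and with it to education and employment. An unadjusted difference between cohorts would mix the effect of adopting FBT with a difference in age created by recruitment.

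**Working it through.** The plan gives no figure for this point, so there is none to reproduce.

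**Inputs from the protocol.** Minimum age at contact: 16. Starts: January 2015 to December 2020, with FBT from 2018. Earliest contact: July 2022. Close: 31 December 2023, the most generous reading of the fourth quarter.

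**Step 1: age floor.** A patient can be contacted by date C only if

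age at start ≥ 16 − (C − start date).

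With C at the end of 2023 (2024.0):

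- January 2015: 16 − 9 = 7.0
- End of 2017 / January 2018: 16 − 6 = 10.0
- January 2020: 16 − 4 = 12.0
- End of December 2020: 16 − 3 = 13.0

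The floor is thus 7-10 years in the earlier cohort and 10-13 in the FBT cohort. If contact took place only at approval in July 2022 (2022.5), every floor rises by 1.5 years, to 8.5-11.5 and 11.5-14.5.

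**Step 2: who is missing from the FBT cohort.** With start dates uniform over 2018-2020 and C at the end of 2023, a patient aged a at start (10 ≤ a ≤ 13) is retained with probability (a − 10)/3. At the midpoints 10.5, 11.5 and 12.5 this gives 17%, 50% and 83%. Weighting by the age distributions in Step 3, where older ages are commoner within each year, gives about 20%, 53% and 85%. Below age 10 nobody is retained, but under-10s are less than 1% of patients in every scenario of Step 3.

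**Step 3: share lost.** This needs an age distribution, which the documents do not give. Assumption: age at start is normal with mean 14-15 and SD 1.6-1.7, truncated to 9-18, with uniform start dates. Simulated results:

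| | Contact to end-2023 | Contact to mid-2023 |
|---|---|---|
| FBT cohort lost | 2.8-9.5% | 5.1-14.8% |
| Earlier cohort lost | at most 0.1% | at most about 0.3% |
| 2020 starters lost | 6-19% | 11-28% |
| Difference in mean age, retained patients | 0.1-0.3 years | 0.15-0.4 years |

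With wider assumptions (mean 13.5-15.5, SD 1.5 or 2.0, lower limit 7 or 10) and contact to the end of 2023, the loss is about 1-18% of the FBT cohort and 0-1.0% of the earlier cohort.

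**Step 4: possible effect on the estimate.** The documents give no age effect either. If the hazard of weight restoration changed by 10% per year of age (assumed), an age shift of 0.1-0.4 years would move an unadjusted hazard ratio by roughly 1.1^0.1 to 1.1^0.4, that is 1-4%. At 20% per year, 1.2^0.1 to 1.2^0.4 gives about 2-8%.

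**The case against.** Four points can be made for the plan.

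First, the final quarter of 2023 is an expected finish and not an eligibility limit. Contact follows each patient's sixteenth birthday, so a later close shrinks the loss. This stands.

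Second, age-adjusted models are already planned, and age is extracted for every participant. Given start date, this exclusion depends on age, so adjustment is the natural remedy. This largely stands. What remains is that those models are described as additional to a model without covariates, and that support in the FBT cohort is thin at ages 10-11, where the estimate leans on the earliest FBT starters or on extrapolation.

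Third, the age shift is small and its effect on the results has not been shown. This also stands. It limits the weight of the point but does not remove the selection.

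Fourth, a reader might infer that the protocol contradicts itself on who may consent. It does not. The ethics requirement accepts participants or guardians, and waiting until patients can consent for themselves satisfies it. The guardian route is permitted but not taken up in the recruitment text.

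**Conclusion.** Followed as written, the plan selects on age differently in the two cohorts. The direction follows from the protocol's own dates and needs no outside assumption. The size does: about 3-10% of the FBT cohort lost by the end of 2023, or 5-15% by mid-2023, against at most about 0.3% of the earlier cohort. These figures rest on an assumed mean age at start of 14-15, an SD of 1.6-1.7 and uniform start dates. Losses are concentrated in the later FBT starters.

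Two stronger readings are tempting. One is that the youngest age groups are absent from the FBT cohort, so that no adjustment could help. Only under-10s are wholly missing; ages 10-12 are thinned, and adjustment for age recovers much of the difference. The other is that all patients under 13 should leave the main comparison. That would remove about 11-28% of patients under the same assumptions, to correct a smaller loss in one cohort, and it would narrow the population studied. The documents support a modest, avoidable imbalance that merits a cheap correction, not a conclusion that the comparison is invalid.

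**What to change.** Preferred: add a guardian-consent route for eligible patients still under 16 during recruitment, as the ethics requirement allows. This removes the selection at its source. The cost is an additional consent form and an ethics amendment.

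If the age-16 rule is kept:

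- Name the already planned age-adjusted model as the main comparison. This costs one sentence in the analysis plan.
- Add a sensitivity analysis restricted to patients aged 13 or over at treatment start in both cohorts, since 13 is the age at which every start year is contactable by the end of 2023. The cost is lower precision in that analysis only.
- Report eligible and included patients by cohort and start year, so that readers can see the actual loss.
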